To observe the efficacy and safety of BENET Tablets 17.5 mg/Actonel Tablet 17.5 mg in patients with osseous Paget's disease up to Week 48 as an all-case surveillance based on the approval conditions.

2. Patients to be included in analyses

(1) Breakdown of patients to be included in analyses

“Patients included in safety evaluation” and “patients included in efficacy evaluation”.

(2) Patients included in safety evaluation

Of the patients from whom a case report form (CRF) is collected, those who satisfy either of the following conditions are excluded from safety evaluation and others are included in safety evaluation.

- i) A patient not administered this drug
- ii) A patient in whom onset of adverse event is unknown
- iii) Of the patients with duplicated enrollment, those who were enrolled later.
- iv) A patient for whom administration was started outside the enrollment period*

* The date of starting administration falls after the enrollment period of January 31, 2016 (on and after February 1, 2016).

(3) Patients included in efficacy evaluation

Of the patients included in safety evaluation, those who satisfy the following conditions are excluded from efficacy evaluation and others are included in efficacy evaluation.

- i) patients from whom the information on efficacy before and after administration was not obtained.

3. Handling of patients

Unless otherwise specified, a patient recorded in a different CRF as a re-administered patient will be tabulated as one patient based on each CRF even if he/she is the same person. When tabulating the same patient as one patient, it should be clarified in “creation method” that tabulation is conducted for “each patient unit”.

4. Data Lock Point

(1) Data Lock Point

Date of starting survey: August 1, 2008

Data Lock Points (DLP) are shown below.

1st: September 30, 2008

2nd: March 31, 2009

3rd: September 30, 2009

4th: March 31, 2010

5th: March 31, 2011

6th: March 31, 2012

7th: March 31, 2013

8th: March 31, 2014

9th: March 31, 2015

10th: March 31, 2016

11th: March 31, 2017

12th: March 31, 2018, re-examination

13th: July 15, 2018, re-examination “(4) Safety analysis 10) Profile Table of serious adverse drug reactions,

11) Profile Table of adverse drug reactions not foreseeable from ‘Precautions’”

5. Tabulation and analysis at each DLP

(1) Patient composition diagram

<Analysis population>

Enrolled patients.

<Preparation method>

- 1) number of study sites
- 2) number of enrolled patients

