Number of target patients, number of patients with onset of adverse drug reactions, percentage (%), and number of occurrences of adverse drug reactions will be tabulated according to the patient demographics shown in Table (3). Presence or absence of adverse drug reactions will be tested according to the patient demographics to investigate the factor that affects safety.

Fisher’s exact test will be used for 2×2 contingency table for comparison of categorical data whereas Cochran-Armitage test will be used for $2 \times c$ contingency table for ordinal categorical data.

Table (3) Patient demographics

Item	Category
Sex	1) M, 2) F, 3) unknown
Age (years)	1) <65 years, 2) ≥ 65 years, 3) unknown
Weight (kg) ^{*1}	1) $<[\text{median}]$, 2) $\geq[\text{median}]$, 3) not measured (unknown)
Administration category	1) Initial administration, 2) re-administration
Dosing period (day)	1) ≤ 56 days, 2) ≥ 57 days, 3) unknown
Diagnosis name (osseous Paget’s disease)	1) monostotic, 2) polyostotic, 3) non-classifiable/ unknown
Morbid period ^{*2}	1) <1 year, 2) ≥ 1 and <5 years, 3) ≥ 5 years, 4) unknown
Complication	1) none, 2) present, 3) unknown

Item	Category
Details of complication ^{*3*4}	1) hypertension, 2) diabetes mellitus, 3) hepatic disease, 4) cardiac disease, 5) renal disease, 6) gastrointestinal disease, 7) other
Hypersensitivity	1) none, 2) present, 3) unknown
Details of hypersensitivity ^{*3}	1) drug, 2) food, 3) other, 4) unknown
History of drug therapy for osseous Paget's disease ^{*5}	1) none, 2) present, 3) unknown
Details of history of drug therapy for osseous Paget's disease ^{*3*5*6}	1) calcitonin preparation, 2) etidronate, 3) this drug (Benet, Actonel), 4) bisphosphonate other than this drug and etidronate, 5) unknown
Concomitant drugs	1) none, 2) present, 3) unknown
Details of concomitant drugs ^{*3*6}	1) osteoporosis agents, 2) anti-inflammatory analgesic, 3) cardiac medication, 4) CNS agents, 5) diabetes medication, 6) gastrointestinal medication, 7) other

*1: determine the calculated value for [median]

*2: morbid period starts on the “day of initial diagnosis of osseous Paget's disease” and ends on the “day of starting administration of this drug”.

*3: tabulate for each category (duplicate tabulation)

*4: classify disease names according to the MedDRA code

*5: tabulate prior therapies of osseous Paget's disease in the prior medication.

*6: classify according to the JAPIC Code (drug data file)

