6) Onset of adverse drug reactions <stratified analysis>

<Analysis population>

Patients included in safety evaluation.

<Preparation method>

The factors in “5) Onset of adverse drug reactions by factors” that show a significant difference ($p < 0.05$) concerning presence or absence of adverse drug reactions will be stratified according to the above Table (3), and each adverse drug reaction will be tabulated according to “2) List of onset of adverse drug reactions/infections (Attachment form 2 of the notification from director of MHLW)”. Factors will be compared between categories according to the types of adverse drug reaction (SOC [system organ class] of MedDRA).

7) Profile of adverse drug reactions after initial administration and re-administration in individual patient

<Analysis population>

Patients included in safety evaluation who receive re-administration irrespective of onset of adverse drug reactions.

<Preparation method>

Presence or absence of adverse drug reactions after the initial administration and re-administration, adverse drug reaction name (SOC, PT), seriousness, number of days up to onset of adverse drug reactions, and outcome

will be recorded for each patient. Patients with “presence” of adverse drug reactions will be shown first, followed by patients with “absence” of adverse drug reactions in the order of case number at the initial administration.

8) Summary of interval of re-administration

<Analysis population>

Patients included in safety evaluation who receive re-administration.

<Preparation method>

Summary statistics will be calculated for number of days from the date of completion of the previous administration (date of completion of initial administration in case of re-administration 1) up to the date of starting re-administration according to the number of re-administration.

Handling of re-administration and calculation of interval of re-administration are shown in section “(8) Other arrangements”.

9) Treatment compliance

<Analysis population>

Patients included in safety evaluation.

<Preparation method>

Number of patients and percentage will be shown for “drugs are taken as instructed (compliance of $\geq 90\%$)”, “sometimes forget taking drugs (compliance of $\geq 67\%$ and $< 90\%$)”, “taking drugs half the time (compliance of $\geq 25\%$ and $< 67\%$)”, “hardly taking the drug (compliance of $< 25\%$)”, and “unknown”.

10) Profile table of serious adverse drug reactions

<Analysis population>

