All patients in spontaneous reporting, literature, drug use surveillance, special drug use survey, clinical trials, post-marketing clinical trials, and a clinical trial conducted by other pharmaceutical company.

<Preparation method>

Concerning serious adverse drug reactions, number of patients will be calculated for each type of adverse drug reactions (according to SOC and PT) by the timing of onset and outcome category shown in Table (2). In case of several occurrences of the same adverse event/adverse drug reaction (LLT) in a given patient, they will be tabulated as one according to the priority order in 4). Events with the same PT but different LLT will be tabulated as separate events.

11) Profile table of adverse drug reactions not foreseeable from “Precautions”

<Analysis population>

All patients in spontaneous reporting, literature, drug use surveillance, special drug use survey, clinical trials, post-marketing clinical trials, and a clinical trial conducted by other pharmaceutical company.

<Preparation method>

Concerning the adverse drug reactions not foreseeable from “Precautions”, number of patients for each types of adverse drug reactions (SOC, PT) will be calculated based on the categories of seriousness, timing of onset, and outcome shown in Table (2). In case of several occurrences of the same adverse event/adverse drug reaction (LLT) in a given patient, they will be tabulated as one according to the priority order in 4). Events with the same PT but different LLT will be tabulated as separate events.

(5) Efficacy analysis

1) Changes in excess serum ALP

<Analysis population>

Patients included in efficacy evaluation. However, patients without baseline data or post-administration data will be excluded.

<Preparation method>

For excess serum ALP, measured value at each time point and percent change from baseline will be calculated and summary statistics and two-sided 95% confidence interval will be shown. A paired t-test will be conducted for percent change and p-value of test results will be shown. Details of handling of data at each time point will be shown in “(8) Other arrangements 5) Data of evaluation time point”.

A graph showing changes in mean \pm standard deviation will be prepared for the measured values at each time point and percent change.

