*1: prior medication (administration within 8 weeks of baseline)

*2: classify according to the JAPIC Code (drug data file)

3) Changes in excess serum ALP (subgroup analysis 2)

<Analysis population>

Patients included in efficacy evaluation who receive re-administration. However, a patient without baseline or post-administration data will be excluded.

<Preparation method>

Changes in excess serum ALP and the percent change at initial administration, re-administration 1 and re-administration 2 will be shown for each patient.

4) Changes in serum ALP

<Analysis population>

Patients included in efficacy evaluation. However, a patient without baseline or post-administration data will be excluded.

<Preparation method>

Serum ALP measured at each time point and percent change from baseline will be calculated and summary statistics and two-sided 95% confidence interval will be shown. Paired t-test will be conducted for percent change and p-value for test results will be shown. Details of handling of data at each time point will be shown in “(8) Other arrangements 5) Data of evaluation time point”.

A graph showing changes in mean ± standard deviation will be prepared for the measured value at each time point and percent change.

A graph showing changes over time will be prepared for serum ALP up to Week 48 and percent change from baseline in all patients. A graph showing changes over time will be prepared for patients who received initial administration alone without re-administration and at initial administration in patients who received re-administration, and a graph showing changes over time will be prepared for re-administration 1 and subsequent administration in patients who received re-administration.

Measured value at each time point and percent change from baseline will be calculated for initial administration in patients who received re-administration, and summary statistics and two-sided 95% confidence interval will be shown. Paired t-test will be conducted for percent change and p-value will be shown for the test result. Measured value at each time point and changes in percent change from baseline will be shown for each patient.

Measured value at each time point and percent change from baseline for initial administration and re-administration 1 will be compared in the same figure and the same graph for each patient who receives re-administration.

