Of the patients whose upper limit of the site reference value* is available among those who receive initial administration, percentage of patients will be calculated in whom post-dose serum ALP is lowered by 10% compared with baseline and <2-fold of the upper limit of the site reference value at each time point.

* In case baseline site reference value is available but post-dose site reference value is missing, complement data with baseline site reference value.

5) Changes in serum ALP (subgroup analysis)

<Analysis population>

i) Patients included in efficacy evaluation. However, a patient without baseline or post-administration data will be excluded.

ii) Patients who received initial administration. However, it is not applicable to administration categories 1 and 2 because they are comparison with the initial administration.

<Preparation method>

Serum ALP will be stratified by the items shown in Table (4), measured value at each time point and percent change from baseline will be calculated and summary statistics and two-sided 95% confidence interval will be shown. Paired t-test will be conducted for percent change and p-value will be shown for the test result.

6) Changes in serum ALP (subgroup analysis 2)

<Analysis population>

Patients included in efficacy evaluation and who receive re-administration. However, a patient without baseline or post-administration data will be excluded.

<Preparation method>

Changes in serum ALP and the percent change at initial administration, re-administration 1 and 2 will be shown for each patient.

7) Changes in bone metabolism markers

<Analysis population>

Patients included in efficacy evaluation. However, a patient without baseline or post-administration data will be excluded.

<Preparation method>

Measured value at each time point and percent change from baseline will be calculated for each item of bone metabolism markers.

Summary statistics will be calculated, paired t-test will be conducted for percent change, and p-value will be shown for the test result. A graph showing changes over time in mean \pm standard deviation will be prepared for the measured values. Details of handling of data at each time point will be shown in “(8) Other arrangements 5) Data of evaluation time point”.

8) Evaluation of pain associated with osseous Paget's disease

<Analysis population>

Patients included in efficacy evaluation. However, a patient without baseline or post-administration data will be excluded.

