<Preparation method>

A cross-tabulation table will be prepared for evaluation of pain associated with osseous Paget's disease before and after administration at each evaluation time point. Details of handling of data at each time point will be shown in “(8) Other arrangements 5) Data of evaluation time point”.

Bowker's test of symmetry will be conducted for changes in severity of pain before and after administration.

Severity of pain will be scored as shown below prior to analysis.

no pain \rightarrow 0, not disturbing \rightarrow 1, tolerable \rightarrow 2, unbearable \rightarrow 3

Number of patients with pain associated with osseous Paget's disease by the site of pain and percentage will be calculated at each time point.

9) Imaging findings

<Analysis population>

Patients included in efficacy evaluation. However, a patient without baseline or post-administration data will be excluded.

<Preparation method>

A cross-tabulation table before and after administration will be prepared for bone morphology, trabecular bone structure, and other abnormal findings by imaging findings (simple X-ray) at each time point. Details of handling of data at each time point will be shown in “(8) Other arrangements 5) Data of evaluation time point”.

In case only “no pain” or “presence of pain” is recorded as evaluation finding after administration without recording of “improved”, “no change”, or “worsened”, evaluation will be made as follows.

Baseline	Post-dose	Evaluation
No pain	No pain	No change
No pain	Presence of pain	Worsened
Presence of pain	No pain	Improved

Baseline	Post-dose	Evaluation
Presence of pain	Presence of pain	Not evaluable

(6) Analysis of patients excluded from safety evaluation

1) List of onset of adverse drug reactions

<Analysis population>

Patients excluded from safety evaluation.

<Preparation method>

Analysis shown in “2) List of onset of adverse drug reactions/infections (Attachment form 2 of notification from director of MHLW)” in “(4) Safety analysis” will be conducted. However, total results from the first reporting up to this report will be combined instead of tabulation for each timing.

2) List of seriousness, date of onset, outcome of adverse drug reactions

<Analysis population>

Patients excluded from safety evaluation.

<Preparation method>

Analysis shown in “4) List of seriousness, date of onset, outcome of adverse drug reactions” in “(4) Safety analysis” will be conducted.

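### The overall ALP and bone-marker t-tests, and the ALP confidence intervals, treat repeat courses of one person as independent patients

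*SAP*

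**What the plan says.** Protocol 5.(2)i) has a person enrolled again each time the drug is re-administered, so each course produces its own CRF. SAP Version 4.1, section 3, sets the default that "a patient recorded in a different CRF as a re-administered patient will be tabulated as one patient based on each CRF", even for the same person. An analysis by person must be declared in its preparation method.

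These analyses declare neither patient unit nor a limit to first courses:

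- 5.(5)1), excess serum ALP: "summary statistics and two-sided 95% confidence interval will be shown. A paired t-test will be conducted for percent change".
- 5.(5)4), serum ALP: "summary statistics and two-sided 95% confidence interval will be shown. Paired t-test will be conducted for percent change".
- 5.(5)7), bone markers: "Summary statistics will be calculated, paired t-test will be conducted for percent change, and p-value will be shown for the test result". No interval is planned here.
- 5.(5)8), pain: Bowker's "test of symmetry will be conducted for changes in severity of pain before and after administration".
- 5.(4)5), adverse drug reactions (ADRs) by factor: "Presence or absence of adverse drug reactions will be tested according to the patient demographics to investigate the factor that affects safety".

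Patient unit is declared only for descriptive output: the demographics in 5.(4)1) and the added columns in 5.(4)2) and 3). The ALP subgroup analyses use first courses only, except for administration categories 1 and 2. The response percentage in 5.(5)4) also uses first courses only. No clustered variance or mixed model appears anywhere.

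**The concern.** The t-test and its interval, Bowker's test, Fisher's test and the Cochran-Armitage test all assume independent rows. Two courses of the same person are unlikely to be independent. The standard errors of the pooled results are then not valid unless the within-person correlation happens to be zero.

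Serum ALP is the primary endpoint, and the overall result in 5.(5)1) and 4) is what a reader will take as the main efficacy figure. Two things are at stake: the precision attached to that figure, and its meaning, because it averages first and later courses. In Table (4), the row for all re-administrations and the row for re-administration 2 onward can also hold several courses of one person.

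**Working it through.** **Step 1: does any rule remove the repeat rows?** SAP 2.(2)iii) excludes "Of the patients with duplicated enrollment, those who were enrolled later". This cannot mean re-administration, because the SAP's own tables by re-administration 1, 2 and 3 onward would then be empty. SAP 5.(8)7) drops efficacy data recorded in an earlier CRF after the next course starts. That trims the earlier course and leaves the later row in place. So the repeat rows stay.

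**Step 2: size for the pooled mean.** The plan fixes no sample size and gives no re-treatment share or correlation, so there is no figure of its own to reproduce. Everything below is an assumption: 100 persons (only the shares matter), m courses per person, within-person correlation ρ of 0.3 to 0.7.

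Design effect = 1 + (Σm²/Σm − 1)ρ. Coverage of a nominal 95% interval = 2Φ(1.96/√design effect) − 1.

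Example, 30 persons with one extra course: Σm = 70 + 60 = 130 and Σm² = 70 + 120 = 190. The design effect is 1 + 0.4615ρ, which is 1.14 to 1.32. Coverage is 93.4% to 91.2%.

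| Scenario | Σm | Σm² | Design effect | Coverage |
|---|---|---|---|---|
| 10 persons, one extra course | 110 | 130 | 1.05-1.13 | 94.4-93.5% |
| 30 persons, one extra | 130 | 190 | 1.14-1.32 | 93.4-91.2% |
| 30 persons, two extra | 160 | 340 | 1.34-1.79 | 91.0-85.7% |
| Table (4) re-administration row, 30 persons with two later courses | 60 | 120 | 1.3-1.7 | 91.4-86.7% |

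At ρ = 0.5 the formula gives a type I error of 7.7% (30 persons, one extra) and 11.7% (two extra). Simulated t-tests with 50 and 100 persons gave 7.7-7.9% and 11.4-11.8%. With one row per person they gave 4.8-5.3% across the scenarios run. At ρ = 0 there is no variance error.

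**Step 3: mixing.** Later courses make up 10/110 = 9%, 30/130 = 23% or 60/160 = 38% of rows. Each 10-point difference between later and first courses moves the overall mean by 0.9, 2.3 or 3.8 points, whatever the correlation.

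**Step 4: late time points.** Two features of the SAP change the picture at Week 48 and, for the second, at the final evaluation point.

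- Truncation removes the Week 48 value of a course when the person is re-treated earlier. If it does so for half of the re-treated persons, the first 30-person scenario becomes 85 persons with one row and 15 with two (Σm = 115, Σm² = 145, coverage 94.1-92.9%). The second becomes 85 with one and 15 with three (130, 220, 92.5-89.2%). If it does so for all of them, each person has one Week 48 row and there is no variance error.
- Table (5) lets a value taken up to 28 days before a course serve as its baseline. The same value precedes the re-start, so it may also stand as a late value of the previous course. It is then the numerator of one percent change and the denominator of the next, which pushes their covariance downwards. The correlation can shrink or turn negative.

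**Step 5: pain and ADR tests.** These are simulated error rates at a nominal 5%, for ρ of 0.3-0.7. Fisher's test assumes a factor that is constant within a person and an ADR risk of 10-20%. Bowker's test assumes one symmetric pain model.

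| Test | 30% with one extra (ρ = 0) | 30% with two extra (ρ = 0) |
|---|---|---|
| Fisher | 3.5-5.8% (3.1-3.9%) | 4.8-9.0% (3.2-4.1%) |
| Bowker | 4.9-6.3% (4.7%) | 6.7-10.4% (4.4%) |

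Factors that can change between CRFs, such as age, weight or concomitant drugs, would move less. The test of initial against re-administration has the same persons on both sides. Ignoring a positive pairing there overstates the variance of the difference, so that test leans conservative.

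**The case against.** The reading of section 3 is hard to dispute. The case against concerns its consequence.

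- **A clean ALP result is already planned.** The initial row of administration categories 1 and 2 in Table (4) gives the mean percent change, 95% interval and t-test for all first courses, for both excess and serum ALP. This stands. A reader might infer that the plan has no valid ALP result; it has one, though only as a subgroup row. Markers and pain have no such row.
- **Nothing is decided on these p-values.** There is no success criterion, and p < 0.05 in 5.(4)5) only triggers the stratified tabulation in 5.(4)6). This also stands and limits the weight of the point.
- **First courses alone should not become the sole headline.** A reader might infer that they should. At Week 48 that would drop persons re-treated early and select towards those who were not. In the scenario of 30 persons with one extra course, half truncated, 85 values replace 115 rows and the interval is √(115/85) = 1.163 times as wide. With full truncation it is 70 against 100, √(100/70) = 1.195 times as wide, with no variance error to cure. Protocol 8.(1) also calls for analysis of all treated patients.
- **The coverage figures are a simple model.** Percent change in excess ALP can have a denominator near zero (5.(8)6) substitutes 0.01 for zero), so a few rows may dominate mean and SD. This is fair: the decimals show the order of magnitude only.

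**Conclusion.** The point holds for the overall t-tests in 5.(5)1), 4) and 7), the overall ALP intervals, and the two Table (4) rows that pool later courses. Their standard errors ignore repeated persons, and the overall means mix first and later courses. If the within-person correlation is positive, the intervals are too narrow. Under the assumptions above, the loss runs from under one to about nine percentage points of coverage.

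Two stronger readings are not supported. A reader might infer that the intervals are too narrow by a known amount at every time point; the documents give neither the re-treatment share nor the correlation, and at Week 48 and the final evaluation point the direction itself is open. A reader might also infer that the pain and ADR factor tests are seriously inflated. They share the unit problem, but with one extra course in 30% of persons they stay near 5%. The display category for re-administration 3 onward does not show that many persons reach it.

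This should be fixed, with medium confidence in its practical size.

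**What to change.** 1. In 5.(5)1), 4) and 7), and in the Table (4) rows for re-administration and re-administration 2 onward, base intervals and p-values on patient-clustered standard errors, or show these results without them. State the number of persons and of CRFs for every pooled result.
2. In 5.(5)1) and 4), refer to the initial row of Table (4) as the ALP result with one row per person. State at Week 48 how many persons lack a first-course value because they were re-treated earlier. Do not make this row the only headline.
3. In 5.(5)8), run Bowker's test on initial-administration CRFs only, with the same Week 48 statement, and tabulate re-administration separately.
4. In 5.(4)5), use a patient-clustered method for all factors, or test the factors other than administration category on initial-administration CRFs. Give administration category a clustered test or no p-value. Name the choice in the SAP.

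The cost is SAP wording and some programming. 5.(8)7) already provides for linking the CRFs of one person, so the cluster identifier should be available. Under the assumptions above, clustered intervals would be wider by the square root of the design effect: √1.14 to √1.32, about 7-15%, with one extra course in 30% of persons, and √1.34 to √1.79, about 16-34%, with two. The row for re-administration 2 onward may hold too few persons for a clustered error to be reliable; showing it without interval and p-value is then the simpler choice.
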